literature published in 2012 showed that the incidence of true allergic reaction to local anaesthetic agents (including lidocaine and other products) was about 1% (0.97%)³⁸. The majority of documented cases of allergy to lidocaine has been attributed to preservatives (such as methylparaben) present in the vials of lidocaine rather than to lidocaine itself. Data from clinical evaluation report the same profile of safety and the same effectiveness in terms of aesthetic result for two HA dermal filler formulations (with and without lidocaine)³⁹. In addition, results showed that the adding of 0.3% of lidocaine does not affect the longevity of HA dermal filler. Studies of characterization of HA gel with lidocaine showed that the presence of lidocaine does not affect the properties of the product being freely released. In fact, in vitro kinetics studies the lidocaine contained in the dermal filler is rapidly released from the gel following injection and then it is metabolized, leaving the remaining product exactly equivalent to the HA dermal filler without lidocaine, and so with equivalent performance and longevity ⁴⁰. A comprehensive review and metanalysis on hyaluronic acid plus lidocaine was recently published⁴¹. Studies of characterization of HA dermal filler with lidocaine and kinetic of lidocaine HCl release have been also performed by manufacturer of PEG-linked HA. Lidocaine HCl was immediately released from hyaluronan hydrogels crosslinked by BDDE and by PEG when immersed in aqueous medium with the same kinetic for both hydrogels. Lidocaine HCl did not interact with hyaluronic acid and the release increased with the time of the incubation. Different concentration in hyaluronan or different crosslinkers (BDDE or PEG) did not interfere with the release of lidocaine. The anaesthetic effect of lidocaine added to medical device gradually declined during the first hour, indicating most lidocaine has been released from the HA gel. This short lasting effect may provide additional subject comfort by alleviating the "frozen face" effect, common after application of dental blocks, which can last longer than 2 hours ²².

The usefulness of lidocaine as ancillary substance is supported also by safety data.

1.3 Summary of the preclinical data

Below a summary of the recent preclinical studies, showing the safety of the product.

Tests	Tests report no.	Results
CYTOTOXICITY DIRECT CONTAC on "Hyaluronic acid hydrogels crosslinked by PEGDE with lidocaine"	Eurofins -BIOLAB Report N°: STULV19AA2725-1 GLP	Not citotoxic
SYSTEMIC TOXICITY TEST on "Hyaluronic acid hydrogels crosslinked by PEGDE with lidocaine"	Eurofins -BIOLAB Report N°: STULV19AA2731-1 GLP	Doesn't cause toxic symptoms and satisfies the requirements of the tests
DELAYED HYPERSENSITIVITY TEST - GUINEA PIG MAXIMISATION TEST on "Hyaluronic acid hydrogels crosslinked by PEGDEwith lidocaine"	Eurofins -BIOLAB Report N°: STULV19AA2731-1 GLP	Not sensiting
SUBCUTANEOUS IMPLANTATION TEST ON "Hyaluronic acid hydrogels crosslinked by PEGDE with lidocaine" - Local and systemic effects (4 weeks)"	Eurofins -BIOLAB Report N°: STULV19AA3839-1 GLP	Causes slight local effects compared to the negative control, 4 weeks after implantation in subcutaneous tissue.
		Doesn't cause significantly different systemic effects compared to the control, 4 weeks after implantation in subcutaneous tissue.
SUBCUTANEOUS IMPLANTATION TEST ON "Hyaluronic acid hydrogels crosslinked by PEGDE with lidocaine" - Local and systemic effects (13 weeks)"	Eurofins -BIOLAB Report N°: STULV19AA3420-1 GLP	Causes slight local effects compared to the negative control, 13 week safter implantation in subcutaneous tissue.
		Doesn't cause significantly different systemic effects compared to the control, 13 weeks after implantation in subcutaneous tissue.
SUBCUTANEOUS IMPLANTATION TEST ON "Hyaluronic acid hydrogels crosslinked by PEGDE with lidocaine" - Local and systemic effects (52 weeks)"	Eurofins -BIOLAB Report N°: STULV19AA2734-1 GL	Causes minimal local effects compared to the negative control, 52 weeks after implantation in subcutaneous tissue.
		Doesn't cause significantly different systemic effects compared to the control, 52 weeks after implantation in subcutaneous tissue.

Matex Lab Switzerland

1.4 Potential risks and benefits

Risks associated with hyaluronic acid

Hyaluronic acid containing fillers are generally well tolerated. The most common adverse events are local pain, brusing, ecchimosys, erythema and bleeding - generally mild and transient. Serious adverse events are rare. Early adverse reactions to hyaluronic acid fillers include vascular infarction and compromise; inflammatory reactions; injection-related events; and inappropriate placement of filler material. Among late reactions are nodules, granulomas, and skin discoloration. Most adverse events can be avoided with proper planning and technique. Detailed understanding of facial anatomy, proper patient and product selection, and appropriate technique can further reduce the risks⁴².

Risks associated with lidocaine

Large data on lidocaine toxicity are available on database as TOXNET, MEDLINE, RTECS (Register of toxic effects of chemical substances). The incidence of side effects is directly proportional to the total dose of local anaesthetic agent injected; low doses are generally well tolerated. The initial symptoms of anaesthetic induced toxicity include light-headedness, circumoral numbness, diplopia, and tinnitus. These effects are generally mild and short-lasting. Serious events include slurred speech, tremors, seizure and respiratory depression.

There are no expected serious risks or complications that may emerge from the administration of the two investigational medical devices (HA and HA+lidocaine) according to treatment schedule defined in this investigational protocol. Therefore, it is expected that benefits from the participation in this investigation will outweigh the theoretical risks.

⁴² Signorini M, Liew S, Sundaram H et al. *Global Aesthetics Consensus: Avoidance and Management of Complications from Hyaluronic Acid Fillers—Evidence- and Opinion-Based Review and Consensus Recommendations*. Plast Reconstr Surg. 2016; 137(6): 961–971.

2. INVESTIGATION OBJECTIVES

2.1 **Primary objective**

The primary objective of this investigation is to assess and compare the pain experienced by subjects during and immediately after injections (recording times: within 1 min and 15-30-45-60 minutes after the injection) of the product under investigation [hyaluronic acid PEG-cross-linked formulated with 0.3% lidocaine: HAL] versus the same product WITHOUT lidocaine [HA], admnistered to subjects with moderate to severe nasolabial folds.

2.2 Secondary objectives

The secondary objectives of this investigation are:

- To assess and compare the safety of HAL and of HA;
- To assess and compare and the efficacy of HAL and of HA injection. Clinical efficacy will be determined by the
 - Global Aesthetic Improvement Scale (GAIS), done by the subject at weeks 2, 12 and 24;
 - Wrinkle Severity Rating Scale (WSRS), done by the blinded evaluating investigator at weeks 12 and 24;
 - o blinded evaluating investigator and subject satisfaction done at week 24;
 - o digital photography done before treatment and at weeks 2, 12 and 24.

3. INVESTIGATION DESIGN

This will be a pre-CE mark controlled, prospective, randomized, blinded evaluator, single centre, split-face clinical investigation.

Each subject will receive both medical devices under investigation, one (HAL) on the one side of the face, the other (HA) on the other side, in randomized fashion.

The products will be administered by the Investigator/Co-Investigator (Treating Investigator), while the evaluations will be done by a Co-Investigator not aware of the side type treatment (Blinded Evaluator).

The investigational plan include a Visit 1, during which subjects will be screened for entry (inclusion/exclusion) criteria; eligible subjects will be treated with the medical devices and followed for the next hour for pain and safety evaluation.

Visit 2, 3 and Visit 4 are schedule after 2 (\pm 2 days), 12 (\pm 10 days) e 24 (\pm 10 days) weeks for the assessment of safety and clinical efficacy.

Subjects prematurely discontinued from the investigation after the treatment will perform an 'Early termination visit', in which procedures scheduled for Visit 4 (24 weeks, final visit) will be performed (whenever feasible). In case of premature discontinuation of the investigation, the Investigator will duly record the reason for premature withdrawal in the appropriate section of the case report form (CRF).

Visit 4 (or the 'Early termination Visit') will represent the conclusion of subject's participation in the investigation.

Adverse events will be recorded during the entire investigational period by investigator's assessment and subjects' spontaneous reporting. Vital signs (blood pressure and heart rate) will be measured at each visit in the investigational site.

The total duration of the investigation for each subject will be 24 weeks. This time frame has been selected basing on literature data related to dermal fillers based on hyaluronic acid.

4. SUBJECTS SELECTION CRITERIA

4.1 Subjects recruitment

Subjects will be recruited among the subjects attending the Unit as consequence of whatever reason.

A total of 52 both gender outsubjects aged 18-75 years with moderate to severe nasolabials folds is extimated for data analysis. A maximum number of 55 subjects may be recruited to account for a rate of performance non-evaluable subjects (no records after treatment) up to 5%.

The investigation will be conducted in one single investigational site in Italy: Dermatology Clinic, Department of Clinical and Experimental Medicine, University of Pisa, Italy. [name], head of the Unit, will be the Principal Investigator.

Subjects to be enrolled in the investigation will be evaluated at the investigational site and, after the signature of the Informed Consent Form, will be screened for inclusion. If eligible, will be recruited to partecipate to the study. All subjects screened will be recorded in the investigation Subjects Screening Log.

The Principal Investigator and/or a co-investigator in the investigational site will verify the suitability of each subject for the participation in the investigation based on acceptable medical history and findings in the clinical examination which comply with the inclusion/exclusion criteria detailed in Section 4.2 and 4.3, respectively.

As soon as the number of subjects defined in the protocol will be achieved, no further subjects will be enrolled in the investigation.

To minimize the event of possible photosensitization, treatment should be avoided in the months with strong sunlight (in Italy, approximately, July and August).

Study timelines: as consequence of the ongoing COVID 19 pandemic, several activities (social, economics and healthcare) are delayed or stopped. Therefore, is not easy to hypothesize the actual times of the study. As supposition, may be that the study will start (first patient in) during the first half year 2021 and will end (last patient out) during the first half year 2022.

4.2 Inclusion criteria

Subjects will be enrolled at Visit 1 (Day 1) if they meet all the following criteria:

- 1. Outsubjects of either sex aged \ge 18 and \le 75 yrs;
- 2. Presence of moderate to severe nasolabials folds (WSRS grade 3-4);
- 3. Reasonable potential benefit from correction;
- 4. Subjects able to understand the full nature and the purpose of the investigation, including possible risks and side effects, able to cooperate with the Investigator and to comply with the requirements of the entire investigation (ability to attend all the planned investigation visits according to the time limits included) based on Investigator's judgement;
- 5. Subjects must voluntarily give written informed consent, adhere to the protocol and report events and concomitant medication for the entire duration of investigation.

4.3 Exclusion criteria

Subjects will **not** be enrolled at Visit 1 (Day 1) if they meet any of the following criteria:

- 1. Pregnant (as determined by a urine pregnancy test at the screening visit) or lactating women. For the entire duration of the investigation, female subjects of childbearing potential (i.e., not permanently sterilised post hysterectomy or tubal ligation status or not postmenopausal from at least one year) must adopt an appropriate method of contraception according to the definition of Note 3 of ICH M3 Guideline*;
- 2. Prior treatment of the face (e.g. other permanent or biodegradable injectable fillers or surgical correction such as a face-lift, etc.) within 3 months prior to entry into the study or planned to undergo such therapy during the study;
- 3. Previous tissue augmentation with permanent implants (e.g., silicone) in the area to be treated;
- 4. Presence of active inflammation, infection (acne, herpes, dermatitis, etc.) or unhealed wound of the face;
- 5. Presence of varices in the area to be treated;
- 6. History of hypertrophic scarring;
- 7. Medical history or clinical examination positive for metabolic or endocrine serious diseases (e.g. uncontrolled diabetes or diabetes complications), anaphylaxis, severe allergies, immune disorders affecting the skin, other local or systemic concomitant diseases that may interfere with healing or with protocol evaluation parameters;
- 8. Use of non-steroidal anti-inflammatory drugs (NSAIDs), analgesics, antiplatelets and anticoagulants in the week before treatment;
- 9. Use of any other treatment or medication that, according to its pharmacological properties and in the opinion of the Investigator, can alter the perception of pain, started in the week before the screening visit;
- 10. Use of narcotic agents, antineoplastics, immunosuppressants or of any other agent that may interfere with healing in the 4 weeks before the screening visit;
- 11. Neurological or psychiatric diseases that may threaten the obtaining of informed consent or the adherence to investigation procedures;
- 12. Ongoing neoplastic (including skin cancer) and/or immunodepressive diseases;
- 13. Subjects with known allergy or hypersensitivity to at least one component of any of the investigational medical devices;
- 14. Ongoing or scheduled during the study radiation, laser, ultrasound, chemical peels treatment in the target area;
- 15. Known hypocoagulability state;
- 16. History of drugs and/or alcohol abuse;
- 17. Subjects unable to measure pain properly by means of a visual analogue scale (VAS);
- 18. Subjects considered to be unsuitable to participate, in the investigators opinion, for any other reason;
- 19. Planned relocation during the study, which would make follow-up visits impossible;
- 20. Concomitant participation in other clinical investigations or participation in the evaluation of any investigational drugs/devices during 3 months before this investigation or previous participation in the same investigation or planned to receive other investigational products during the study.

*Note: According to the definition of Note 3 of ICH M3 Guideline a highly effective method is defined as those which results in a low failure rate (i.e. less than 1% per year) when used consistently and correctly.

Highly effective birth control methods include: combined (estrogen and progestogen containing) hormonal contraception associated with inhibition of ovulation (oral, intravaginal, transdermal); progestogen-only hormonal contraception associated with inhibition of ovulation (oral, injectable, implantable); intrauterine device (IUD); intrauterine hormone-releasing system (IUS); bilateral tubal occlusion; vasectomised partner; sexual abstinence.

5. TREATMENTS

5.1 Reference and Test investigational medical devices

Reference device: HA (PEG cross-linked hyaluronic acid hydrogel)

Prefilled sirynge 1 mL.

Packaging: carton box containing one sterile syringe, one 21Gx16 mm needle and a 22Gx50 mm cannula.

Composition: gelatinous, transparent, colourless, cross-linked hydrogel with 2.8% of Hyaluronic Acid and Non-pyrogenic water 97.2% (containing Glycine and L-Proline < 2%).

Handling and storage: the shelf life of the medical device is three years and the products must be protected from damage, freezing and sunlight and stored at a temperature between $+ 4^{\circ}$ C and 27° C.

**Test device** : **HAL** (PEG cross-linked hyaluronic acid hydrogel plus lidocaine)

Prefilled sirynge 1 mL.

Packaging: carton box containing one sterile syringe, one 21Gx16 mm needle and a 22Gx50 mm needle.

Composition: gelatinous, transparent, colourless, cross-linked hydrogel with 2.8% of Hyaluronic Acid and Non-pyrogenic water 96.9% (containing Glycine and L-Proline < 2%) and 0.3% lidocaine.

Handling and storage: the shelf life of the medical device is three years and the products must be protected from damage, freezing and sunlight and stored at a temperature between $+ 4^{\circ}$ C and 27° C.

Both devices are manifactured and will be provided by Matex Lab S.p.A. ([name]. [contact]).

Matex Lab S.p.A. is a company established in 2012 with wide experience in the field of biomedical technologies, specializing in the development of hydrogels for medical purpose.

5.2 Dosage and administration

The investigational medical devices must be administered only to subjects selected for taking part in the investigation according to the protocol.

Duration of treatment

Single admnistration of each device (one on right side and the other on the left side of the face).

Dosage and mode of treatment

- study devices will be administered using linear threading, multiple punctate pools, and/or fanlike injection technique. The technique of injectiom and the depth of injection will be at the discretion of the Treating Investigator; however, for a given subject, both devices will be injected at the same depth and with the same technique.
- in all subjects the first injection will be done in the right side of the face, the second in the left side.
- doses: the minimum amount must be at least 0.5 ml per side, the maximum 2 ml per side, per each implant. The Treating Investigator will decide the dose to obtain the optimal correction of defect per each patient implant.

5.3 Packaging and labelling

The labelling of the investigational product will be performed in accordance with the ISO 14155 guideline for medical devices and all local requirements.

Each single box will be labelled with almost the following information:

- clinical investigational plan code, sponsor's references,
- study site identification,
- Principal Investigator's name,
- product identification,
- batch number and expiry date
- storage conditions,
- the statement 'for clinical study only',
- the statement 'keep out from children',
- place to write the subject code,
- place to write the administration date .

Example:

	Clinical Trial HA28L/MD01/20		
Matex Lab Switzerland SA,[name]			
[contact]			
Study site	Clinica Dermatologica, Dipartimento di Medicina Clinica e Sperimentale		
	Azienda Ospedaliera Universitaria Pisana		
	[name]		
Principal Investigator	[name]		
Product	(HA or HAL)		
batch number/expiry date	XXX/XXXX*		
	Subject n°		
Da	te of admnistration		
For clinical study only. Keep store of	out from children . Protect from damage, freezing and sunlight; at a temperature between + 4° C and 27°		

Each siringe will be labelled almost with the product identification, the study code and a place to write the subject code.

An autoadesive flag label reporting the same data (to be sticked on CRF) is foreseen.

The Investigator and/or Hospital Pharmacist will be responsible for the correct storage and distribution of the investigational medical device, as well as of its accountability.

The Sponsor of the investigation will be responsible for the investigational medical device shipment to the Hospital Pharmacy.

An adequate amount of investigational devices will be supplied to the investigational site. Reserve units will be supplied in case of damaging of the scheduled units.

At the end of the investigation, following a final reconciliation on products accountability, both the used and the unused investigational medical devices will be sent to the Sponsor or locally destroyed at the investigational study site according to the local standard operating procedures (SOPs).

5.4 Treatment code

A computer-generated randomization list (specifying the type of medical devices to be injected in the right and the left side of the face) will be available.

Each subject included in the investigation will be coded by the Investigator through a 2-digit progressive *Screening number* as they present themselves for the investigation at the screening visit (Visit 1), starting from code 01 preceded by the letter "S" (first subject enrolled: code S01).

If a subject discontinues from the investigation, the screening number will not be re-used, and the subject will not be allowed to re-enter the investigation.

Eligibility confirmed, a randomization number will be done starting from 01 (first subject randomized: code 01).

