6.1 Investigation schedule, visits plan and procedures

Visit 1 (Day 1): Screening visit/treatment

Potential participants will be informed orally and in writing about the scope of the investigation, the relevant procedures, the nature of the risks related to the investigation, and they will be asked to sign and date the Written Informed Consent form.

After the correct obtaining of the Informed Consent form, the following assessments and procedures will be performed:

- Demographic data (age, gender, race) will be recorded;
- General medical history will be recorded;
- A general physical examination will be performed, including the measurement of height and weight. Any abnormality identified at the screening visit (Visit 1) should be recorded in the subject's medical records and in the CRF;
- All concomitant medications taken by the subject (including those taken in the prior one week) will be recorded in the subject's medical records and in the appropriate section of the CRF;
- Vital signs (blood pressure and heart rate) will be measured and recorded;
- An urine pregnancy test will be performed in female subjects of childbearing potential (i.e., not permanently sterilised post hysterectomy or tubal ligation status or not postmenopausal from at least one year);
- The digital photo will be done;
- The WSRS will be done;
- Eligible subjects will be included in the investigation and treatments will be done. HAL will be injected on the one side of the face, HA on the other side –by the Treating Investigator . Treatment procedure:
 - 1. Check the randomization list for the type of product (HAL or HA) to be injected in the **RIGHT** side of the face;
 - 2. Take the selected product box;
 - 3. Write the subject number and the date of admnistration on the label;
 - 4. Open the box and pick-up the siringe;
 - 5. Detach the flag label and stick it on the appropriate space present in the CRF (label not available in consequence of whatever reason, a withness will write the product code –HA or HAL- in the space, dating and signing it);
 - 6. Disinfect the skin thoroughly with iodopovidone or chlorhexidine disinfectant.;
 - 7. Screw the needle firmly onto the luer-lock connection of the syringe;
 - 8. Press gently on the plunger in order to expel any residual air from the device;
 - 9. If the needle is obstructed, do not increase pressure on the plunger but change the needle;
 - 10. Perform the injection;
 - 11. Record in the CRF the volume injected;

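### The side assignment is read straight from a sequential list with no concealment step, so the next right/left assignment can be known before a subject is enrolled

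*Combined protocol and SAP*

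**What the plan says.** Section 5.4 announces a computer-generated list "specifying the type of medical devices to be injected in the right and the left side of the face". It names no holder and no format. Once a subject is found eligible, "a randomization number will be done starting from 01", so rows are used in order.

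Section 6.1 (Visit 1, treatment procedure) opens with the instruction "Check the randomization list for the type of product" for the right side. The next step is to take the matching box. Under section 5.3, boxes and syringes carry the product identity, HA or HAL, so there are no coded kits behind the list.

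On roles, section 4.1 states: "The Principal Investigator and/or a co-investigator in the investigational site will verify the suitability of each subject for the participation in the investigation". Section 3 gives the injections to the Investigator or Co-Investigator acting as Treating Investigator. Only the Blinded Evaluator is described as unaware of the side.

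Eligibility leaves room for judgement. Inclusion criterion 3 is "Reasonable potential benefit from correction", and exclusion criterion 18 removes "Subjects considered to be unsuitable to participate, in the investigators opinion, for any other reason". Section 4.1 recruits from people attending the unit for any reason and sets no order of approach.

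**The concern.** In a split-face trial, randomization has to keep product unrelated to which fold is deeper or harder to correct. Pairing removes differences between subjects. It does not remove a link between product and side within a face, because that link sits inside the paired difference. Only random assignment of side that cannot be foreseen breaks it.

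If the next row can be read in advance, a subject whose right fold is clearly deeper could be taken now, approached later, or judged unsuitable, depending on which product is due on the right. Baseline severity could then differ by product. The comparisons most exposed are WSRS by side and global satisfaction by side at week 24. Pain is exposed only indirectly. Section 5.2 lets the Treating Investigator choose 0.5 to 2 ml per side to obtain optimal correction, so a deeper fold may receive more injection.

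**Working it through.** **1. The passages side by side**

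| Question | What the documents give |
|---|---|
| Who holds the list? | Not stated (5.4) |
| How is one assignment released? | By reading the list (6.1, step 1) |
| Are later rows hidden? | No envelope, web, telephone or pharmacy release is described |
| Is the order predictable? | Yes, sequential from 01 (5.4) |
| Does product coding add a barrier? | No, labels read HA or HAL (5.3) |
| Are list reader and eligibility assessor separated? | No; both tasks fall to Investigator/Co-Investigator roles (3, 4.1) |
| Is baseline by side adjusted for? | Not specified; secondary endpoints get a Wilcoxon signed-rank test and baseline is described only (10.2.5) |

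Section 5.4 fixes when a number is given. It does not fix when the list may be seen. Anyone who has looked up one subject's row can also see the next, unless something hides it.

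**2. The plan's own figures (10.2.1)**

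Inputs: n = 52, paired difference 1.0, SD of differences 2.5, two-sided alpha 0.05. Noncentrality = (1.0/2.5) × √52 = 2.88 on 51 degrees of freedom. Exact power is 80.8%, which agrees with the stated 81%. The ceiling is 52/(1 − 0.05) = 54.7, rounded up to 55, as stated. Concealing the list changes neither figure.

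**3. Possible size on baseline WSRS (assumptions)**

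Let f be the share of subjects whose folds differ by g grades, and p the probability that the deeper fold receives a given product. The expected baseline difference between products is f × [p − (1 − p)] × g = f(2p − 1)g. Entry allows grades 3 and 4, so take g = 1. The documents give neither f nor p. With f = 0.3 assumed:

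- p = 0.5 (no steering): 0.3 × 0 × 1 = 0
- p = 0.7: 0.3 × 0.4 × 1 = 0.12 grade
- p = 1 (complete steering): 0.3 × 1 × 1 = 0.30 grade

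The result is proportional to f. For comparison, the chance standard error of this difference under concealed 50:50 assignment is √(0.3/52) = 0.076 grade. A value of 0.12 is 0.12/0.076 = 1.58 standard errors, which is reached or exceeded in either direction in about 11% of fully concealed trials (normal approximation).

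**4. Possible size on pain (assumptions)**

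Suppose there is no true effect and steering shifts the mean paired difference by b, in the units of section 10.2.1. With n = 52 and SD 2.5, the two-sided test rejects with these probabilities:

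| b | Rejection rate |
|---|---|
| 0.1 | 5.9% |
| 0.25 | 10.9% |
| 0.5 | 29.3% |
| 1.0 | 80.8% |

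Nothing in the documents says which b, if any, would arise.

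**The case against.** The best defence is that the written order is already the right one. Section 6.1 lists the photograph and the WSRS first, then inclusion of eligible subjects, and only then the check of the list. Baseline WSRS is scored per side by the blinded evaluator (section 7), so the grade itself is hard to manipulate. The Screening Log (4.1) and the subject registry (14.2.1) would show a consented subject who was passed over. Each subject receives both products, so selection between subjects cancels. GAIS is scored against the pre-treatment state, so a baseline difference does not carry into it directly. A WSRS imbalance would be visible in the data, and 0.12 grade lies within ordinary chance variation.

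Much of this stands. It narrows the route to left-right asymmetry combined with reordering, deferral or exclusion, and it rules out 0.12 grade as an estimate of the bias. It does not close the route. The written order does not stop the next row being read beforehand. The log begins after consent, so deferral before consent leaves no trace. The blinded evaluator controls the grade, not who is enrolled next. Chance imbalance is already covered by the test's error rate, whereas a systematic shift is not.

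A reader might go further and infer that the list is one open page, that a single small team does everything, or that the site does know each coming assignment and matches folds to products. The documents do not say so. They give no format, no team size and no such practice. They support only that advance knowledge is possible and nothing prevents it.

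**Conclusion.** The procedure in sections 5.4 and 6.1 leaves allocation unconcealed. This is more than a missing detail, because step 1 describes direct reading of a sequential list as the method. Bias requires three things together: folds that differ, advance sight of the next row, and action on it through the order of approach or a discretionary criterion. The last two are possibilities inferred from the text, not described events.

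The size is unknown. Under the assumed 30% asymmetry, the baseline WSRS difference between products could lie anywhere from 0 to 0.30 grade in either direction. The effect on pain depends on an unstated link between fold depth and injected volume. The finding therefore does not show that the primary result would be biased. It shows that a standard protection is absent and that the analysis in section 10.2.5 specifies no adjustment for baseline by side. The change is worth making before the first subject is randomized. Confidence is medium.

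**What to change.** In section 5.4 and step 1 of section 6.1, replace direct reading of the list with sequentially numbered, opaque, sealed envelopes, or with release by subject number from a list holder independent of enrolment. The Treating Investigator opens each assignment only after eligibility is signed and the blinded evaluator's baseline WSRS for each side is in the CRF. Date and time of opening are recorded. If such a step already exists in practice, the sponsor need only write it into these two sections.

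The cost is about 55 envelopes, a change of wording and one more item for the monitor to reconcile. The sample size (52, ceiling 55), power, visits and staff are unchanged. The change conceals allocation before enrolment only. It does not blind the Treating Investigator at injection, and it does not remove the HA/HAL flag labels that step 5 of section 6.1 puts in the CRF; those are separate blinding questions.
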